**Table 1. Representative Dosing Schedule**

Day	M	T	W	Th	F
Week 1	Subject 1	Subject 2	Subject 3	Subject 4	Subject 5
Session	1	1	1	1	1
CBD (mg)	0	200	400	800	0
Week 2	S1	S2	S3	S4	S5
Session	2	2	2	2	2
CBD (mg)	200	400	800	0	200
Week 3	S1	S2	S3	S4	S5
Session	3	3	3	3	3
CBD (mg)	400	800	0	200	400
Week 4	S1	S2	S3	S4	S5
Session	4	4	4	4	4
CBD (mg)	800	0	200	400	800

Based on CBD's long half-life (21-33 hrs) (Consroe et al., 1998), sessions will be separated by at least 5 days to allow for CBD clearance and prevent carryover effects. Physiological effects (heart rate and blood pressure) and side effects will be monitored throughout the session.

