### III. General Investigational Plan

This within-subject, double-blind, placebo-controlled study will assess the analgesic effects of a range of cannabidiol (CBD) doses (0, 200, 400, or 800 mg, po). Normal, healthy volunteers with no current pain or substance use will participate in 4 outpatient laboratory sessions over the course of 4 weeks during which the analgesic effects of CBD will be assessed using the Cold-Pressor Test (CPT), a laboratory model of pain which has predictive validity for the clinical use of analgesics. The order of CBD dose will be counter-balanced across participants; **Table 1** illustrates a representative dosing schedule. Secondary measures will include subjective and physiologic effects of CBD, and the CPT, subjective mood and drug effects, and vital signs will be measured before and at specified time points after CBD administration. Determining the efficacy of CBD in an experimental model of pain will provide important endpoints (i.e., dose, time course) of this effect to further investigate the potential role for clinical use of CBD as an analgesic.

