**Table 1. Representative Dosing Schedule**

Day	M	T	W	Th	F
Week 1	Subject 1	Subject 2	Subject 3	Subject 4	Subject 5
Session	1	1	1	1	1
CBD (mg)	0	200	400	800	0
Week 2	S1	S2	S3	S4	S5
Session	2	2	2	2	2
CBD (mg)	200	400	800	0	200
Week 3	S1	S2	S3	S4	S5
Session	3	3	3	3	3
CBD (mg)	400	800	0	200	400
Week 4	S1	S2	S3	S4	S5
Session	4	4	4	4	4
CBD (mg)	800	0	200	400	800

The primary outcome measures for this study will be the dose-dependent analgesic and subjective effects of CBD. There will be 4 dose conditions under which these endpoints will be measured (0, 200, 400, and 800 mg CBD). A priori planned comparisons will be performed to determine dose-dependent effects of CBD relative to placebo. We hypothesize that CBD will elicit dose-dependent increases in analgesia. We also hypothesize that CBD will fail to produce subjective effects of intoxication ('Solution liking,' 'Good solution effect,' etc.).

IV. Protocol

*PARTICIPANTS:*

All research volunteers (N=18) will be between 21 and 50 years old, male or non-pregnant female, and healthy (according to medical and psychiatric examinations). It is expected that 50% of applicants will be female and that 40-50% of applicants will be non-Hispanic Caucasian, 25-30% will be Hispanic, 15-20% will be non-Hispanic Black or African American, 5-10% will be Asian or Pacific Islanders, and less than 1% will be Native Americas, Eskimos, or Aleuts. We will not accept volunteers who are substance-users, on parole or probation, nor those previously convicted of a crime of violence. The extensive medical screening assures that only healthy volunteers will be used. Any subject with abnormal medical findings will be offered referral for treatment. Likewise, if an individual is dependent on any drugs, with the exception of nicotine or caffeine, he/she will be offered referral to an appropriate treatment program.

*STUDY INCLUSION AND EXCLUSION CRITERIA* (list in outline form):

INCLUSION CRITERION	METHOD OF ASCERTAINMENT
1. Adults between the ages of 21 and 50	Clinical interview and verification with identification
2. Able to perform study procedures	Practice sessions
3. Women practicing an effective form of birth control (condoms, diaphragm, birth control pill, IUD)*	Self-report during interview
EXCLUSION CRITERION	METHOD OF ASCERTAINMENT
1. Female subjects who are currently pregnant or breastfeeding	Clinical interview, physical examination, serum HCG

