### **Laboratory Sessions and Cold Pressor Test (CPT):**

In the current study, there will be four laboratory sessions to assess the effects of a range of cannabidiol doses on analgesia. During the CPT test sessions, which will start and end at approximately 0900 and 1630hr, the analgesic, subjective, and physiological effects of cannabidiol will be determined repeatedly following a pretreatment of cannabidiol or placebo (see **Table 3**). Administration of cannabidiol will occur at 1000 hr. Baseline assessments will include measurements of analgesia (CPT), mood, blood pressure and heart rate. A breathalyzer test will be done before each session and urine samples will be tested for illicit drug use and, for women, pregnancy (prior to all sessions). Participants testing positive for drugs will be excluded from further participation. A light breakfast will be provided before CBD administration (e.g., bagel, juice, coffee).

The CPT, a well-established model for producing pain in humans (e.g., Chen et al., 1989; Conley et al., 1997; Zacny et al., 1996), will be performed once before and six times after drug administration and will last approximately 15 minutes. Our laboratory and others have shown that multiple CPTs can be carried out within the same day with little or no carryover effects between tests (e.g., Conley et al., 1997; Zacny et al., 1996), and it can be used to detect the analgesic effects of cannabinoids (Cooper et al., 2013). In this assay, the two dependent measures are latency to feel pain and latency to withdraw the hand from the cold water. Because previous research has shown that experimenters of the opposite sex influence responding to painful stimuli (Clark and Goodman, 1974; Clark and Mehl, 1971; Levine and De Simone, 1991), the sex of the experimenter will always be of the same sex as the research participant.

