*Laboratory Facility:* All experimental sessions will be conducted in the Substance Use Research Center (SURC) located on the 3rd floor of the NYS Psychiatric Institute. Participants will sit in a comfortable task chair in front of a Macintosh computer. A response manipulandum (“mouse”) will be used for completion of pain rating scales and subjective-effects questionnaires.

**Table 2.** Session Schedule

Time (hr)	TIME (min)	EVENT
0900	-60	Urine, breathalyzer, breakfast
0930	-30	Baseline assessments: Mood scales, CPT
1000	0	Solution administration
1030	30	BP/HR, SRF, Mood scales
1100	60	SRF, Mood scales, CPT
1130	90	BP/HR, SRF, Mood scales
1200	120	SRF, Mood scales, CPT
1230	150	BP/HR, SRF, Mood scales
1300	180	SRF, Mood scales, CPT
1330	210	BP/HR, SRF, Mood scales, Lunch
1400	240	SRF, Mood scales, CPT
1430	270	BP/HR, SRF, Mood scales
1500	300	SRF, Mood scales, CPT
1530	330	BP/HR, SRF, Mood scales
1600	360	SRF, Mood scales, CPT
1615	375	BP/HR, SRF, Mood scales
1630	390	BP/HR, Field Sobriety Test, participant discharge

**Table 3.** Events Occurring During the Cold-Pressor Test

TIME (sec)	EVENT
-190	ST, Warm tank immersion, State
-10	ST, Vital Signs
0	Cold water immersion
180 or When hand is withdrawn	ST, Vital Signs, Pain Intensity/Bothersomeness Scales, CPT-VAS, SF-MPQ, State

*ST=skin temperature      Vital signs=blood pressure and heart rate      CPT-VAS=Visual Analog Scales  
 State=State Anxiety Inventory      SF-MPQ=Short-Form McGill Pain Questionnaire\**

*\*See descriptions of questionnaires above.*

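### The only dose orders the plan shows balance session position but not the preceding dose; a Williams square would do both at no cost to the planned analysis

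*Combined protocol and SAP*

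**What the plan says.** The General Investigational Plan (section III) states: "The order of CBD dose will be counter-balanced across participants". It gives no list of sequences, no type of square and no randomisation of participants to sequences. The only orders shown are in Table 1, printed twice under the title "Table 1. Representative Dosing Schedule": Subject 1 has 0-200-400-800 mg, Subject 2 has 200-400-800-0, Subject 3 has 400-800-0-200, Subject 4 has 800-0-200-400, and Subject 5 repeats Subject 1. The planned number is 18.

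On carry-over, the text below the second printing of Table 1 (section IV, Medication) cites a half-life of 21 to 33 hours and says that "sessions will be separated by at least 5 days to allow for CBD clearance and prevent carryover effects". Table 1 draws the sessions one week apart.

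The Statistical Analysis Plan uses repeated measures ANOVA and compares each active dose with placebo. Pain threshold, tolerance and pain ratings are changes from the pre-dose value of the same session. No session, sequence or preceding-dose term is named.

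On pre-dose measurement, section III says that "subjective mood and drug effects, and vital signs will be measured before and at specified time points after CBD administration". The text on laboratory sessions says: "Baseline assessments will include measurements of analgesia (CPT), mood, blood pressure and heart rate". The pre-dose row of Table 2 reads "Baseline assessments: Mood scales, CPT", and the Solution Rating Form (SRF) first appears in that table at +30 minutes.

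**The concern.** Counter-balancing can mean balance over session position, over the preceding dose, or both. The orders in Table 1 give the first for each set of four participants and not the second: 200 mg only ever follows placebo, 400 mg only 200 mg, 800 mg only 400 mg, and placebo only 800 mg. Any effect left over from the previous session is then tied to the current dose, and it falls most heavily on the placebo session, which is the reference for all three planned comparisons.

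At stake are two modest things. One is a small avoidable bias if the washout is not complete for some outcome. The other is the ability to report a dose comparison adjusted for the preceding dose without a large loss of precision. The planned, unadjusted analysis loses no precision under the cyclic orders.

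The outcomes most exposed are the SRF items, which bear on the hypothesis that CBD does not produce intoxication. If the SRF has no pre-dose value, it cannot be analysed as a change within the session.

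**Working it through.** **Inputs from the documents.** Doses 0, 200, 400 and 800 mg in four sessions; the orders in Table 1; N = 18; half-life 21 to 33 h; gap of at least 5 days (120 h), drawn as 7 days (168 h); measurement times from Table 2. The plan states no figure for carry-over or for sample size that could be reproduced first.

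**Ordered pairs.** Four doses give 4 × 3 = 12 ordered pairs of different doses. Table 1 contains only 0→200, 200→400, 400→800 and 800→0, so 4 of 12. The Williams square 0-200-800-400, 200-400-0-800, 400-800-200-0, 800-0-400-200 contains all 12, once each.

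**Residue of the previous dose.** Fraction left = 0.5^(gap / half-life).

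- 5 days: 0.5^(120/33) = 0.080; 0.5^(120/21) = 0.019
- 7 days: 0.5^(168/33) = 0.029; 0.5^(168/21) = 0.004

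**Mean preceding dose** over the four positions, counting the first session as 0, in balanced sets of four:

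- Cyclic: placebo (0 + 3 × 800)/4 = 600 mg; 200 mg 0; 400 mg (3 × 200)/4 = 150 mg; 800 mg (3 × 400)/4 = 300 mg. Differences from placebo: −600, −450, −300 mg.
- Williams: each dose d follows each other dose once, so the mean is (1400 − d)/4 = 350, 300, 250, 150 mg. Differences from placebo: −50, −100, −200 mg.

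Eighteen is not a multiple of four, so these are approximate for this trial. With sequences used 5/5/4/4 times and participant and session effects fitted, one allocation gives −577/−441/−286 mg (cyclic) and −65/−75/−209 mg (Williams).

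**Residue carried into the dose contrasts.** Assumptions: residue is proportional to dose, decays exponentially, and comes from the last dose only. The unit is dose-equivalents, not a measured amount of drug and not an effect on ratings. In the least favourable case (33 h, 5 days):

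- SRF without a pre-dose value, averaged over the 13 times from +30 to +375 min (mean fraction 0.0748): −45/−34/−22 mg cyclic, −3.7/−7.5/−15 mg Williams, for 200/400/800 mg.
- Pain change score: the fraction is 0.0813 at −30 min and averages 0.0747 over +60 to +360 min, a change of −0.0065. Times −600/−450/−300 this is about +3.9/+2.9/+2.0 mg cyclic.

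At 7 days and 33 h, the cyclic SRF figures fall to −16/−12/−8.2 mg. At 7 days and 21 h they are −2.1/−1.6/−1.0 mg.

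**Precision.** Least squares with participant, session and dose effects, N = 18, over all 5/5/4/4 splits. Variance of active minus placebo in units of σ², the within-participant variance:

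| Model | Cyclic | Williams |
|---|---|---|
| No preceding-dose term | 0.111–0.112 | 0.111–0.112 |
| Categorical preceding dose | 0.553–0.684 (SE ×2.23–2.48) | 0.121–0.126 (SE ×1.04–1.06) |
| Linear preceding dose, 200 mg | 0.518–0.631 (SE ×2.16–2.38) | all three doses: 0.112–0.125 (SE ×1.00–1.06) |
| Linear, 400 mg | 0.348–0.394 (SE ×1.77–1.88) | |
| Linear, 800 mg | 0.212–0.244 (SE ×1.38–1.48) | |

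**What a Williams square cannot do.** Under the linear term, its 800 mg carry-over effect has an SE of about 0.40 σ. Two SEs are 0.80 σ. If carry-over effect is proportional to residue, the direct effect of 800 mg would have to be about 0.80/0.080 = 10 σ (5 days, 33 h) or 0.80/0.029 ≈ 28 σ (7 days, 33 h) for carry-over to reach that size.

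**The case against.** The strongest reply is that no defect is shown. The table is labelled representative, counter-balancing does not promise balance of the preceding dose, little drug remains after the washout, and the plan proposes no preceding-dose model whose precision could suffer. Most of this stands. It limits the point to a design improvement, but the improvement is specific and free before sessions start.

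Three stronger readings are tempting, and the documents do not support them.

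- A reader might infer that all 18 participants followed the cyclic orders. The full allocation is not given, so this is unknown.
- A reader might infer that a Williams square would verify the washout. The SE of about 0.40 σ shows that it would not, for carry-over of the size argued here. Equally, carry-over is estimable under the cyclic orders, only inefficiently, and the 2.5-fold figure is the upper end for a categorical term.
- A reader might infer that section III and Table 2 contradict each other on pre-dose drug-effect ratings. They need not. The pre-dose cold pressor test includes the CPT-VAS (Table 3), with items such as feeling drunk, elated or sedated, and this may already satisfy section III. Items that rate the solution may have been left out before dosing on purpose. The form itself is in an appendix that was not supplied.

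It is also fair that the SAP is written in the past tense, so the change to the allocation may come too late. The reporting part of the fix does not depend on that.

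**Conclusion.** The point holds as a low-cost design and reporting improvement. The orders shown leave the preceding dose fully confounded with the current dose apart from first sessions, and the plan's wording does not rule this out for the full allocation. If these orders are used throughout, mean preceding dose differs from placebo by 600/450/300 mg for 200/400/800 mg, against about 50/100/200 mg in a Williams square, and an adjusted dose comparison becomes expensive where it could cost about 6% in SE.

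The documents do not show that any result is biased. Residue is 0.4% to 8% of the previous dose, pain change scores are nearly protected, and whether the residue moves any solution rating, and in which direction, is unknown. The gain from a Williams square is less potential carry-over bias and an affordable adjustment. It is partial: for 800 mg, 200/300, or about two thirds, of the cyclic imbalance remains unless preceding dose is in the model.

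The figures rest on the plan's half-life, first-order decay, residue proportional to dose, first-order carry-over, 18 complete participants and a near-equal split over four sequences.

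**What to change.** If sessions have not started: randomise participants to the four sequences of a 4 × 4 Williams square, for example the one given above, and state the allocation for all 18. Add a sensitivity model with session number and preceding dose. Doses, visits and number of participants stay the same. The cost is a different pharmacy allocation list and one extra model.

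If sessions are complete: tabulate the orders and between-session intervals actually used, and run the same sensitivity model. If the orders were cyclic, say plainly that its precision is low. The cost is one table and one model.

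In either case, add a sentence stating whether the SRF has a pre-dose value and whether it is analysed as a change or as raw ratings. If the pre-dose CPT-VAS is what section III refers to, say so.

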### **Laboratory Sessions and Cold Pressor Test (CPT):**

In the current study, there will be four laboratory sessions to assess the effects of a range of cannabidiol doses on analgesia. During the CPT test sessions, which will start and end at approximately 0900 and 1630hr, the analgesic, subjective, and physiological effects of cannabidiol will be determined repeatedly following a pretreatment of cannabidiol or placebo (see **Table 3**). Administration of cannabidiol will occur at 1000 hr. Baseline assessments will include measurements of analgesia (CPT), mood, blood pressure and heart rate. A breathalyzer test will be done before each session and urine samples will be tested for illicit drug use and, for women, pregnancy (prior to all sessions). Participants testing positive for drugs will be excluded from further participation. A light breakfast will be provided before CBD administration (e.g., bagel, juice, coffee).

The CPT, a well-established model for producing pain in humans (e.g., Chen et al., 1989; Conley et al., 1997; Zacny et al., 1996), will be performed once before and six times after drug administration and will last approximately 15 minutes. Our laboratory and others have shown that multiple CPTs can be carried out within the same day with little or no carryover effects between tests (e.g., Conley et al., 1997; Zacny et al., 1996), and it can be used to detect the analgesic effects of cannabinoids (Cooper et al., 2013). In this assay, the two dependent measures are latency to feel pain and latency to withdraw the hand from the cold water. Because previous research has shown that experimenters of the opposite sex influence responding to painful stimuli (Clark and Goodman, 1974; Clark and Mehl, 1971; Levine and De Simone, 1991), the sex of the experimenter will always be of the same sex as the research participant.

The cold pressor apparatus will consist of two coolers filled with either warm (37°C) or cold (4°C) water with an aquarium pump that will circulate the water. The CPT will be performed seven times throughout the session. At the beginning of each CPT trial, the experimenter will read a standardized script describing the procedures to the participant. The participant will begin the test by placing the left hand into the warm water for three minutes. During the warm water immersion, the State Anxiety Inventory will be completed; blood pressure and heart rate will be measured. The participant will be instructed to remove his or her hand from the water after three minutes and skin temperature of the thumb pad will be measured. Another scripted statement will be read describing the CPT procedure to the participant, before the participant immerses his or her hand in the cold water. Participants will be instructed to report the first painful sensation, and to remove the hand when the stimulus can no longer be tolerated. Immediately after removing the hand from the cold water, blood pressure, heart rate, and skin temperature will then be measured. Upon withdrawal of the hand, participants will be asked to rate the pain and bothersomeness of the cold-water stimulus on a scale from 0 to 10, 0 being "not painful/bothersome at all" and 10 being "most painful/ bothersome feeling imaginable." They will additionally complete a shortened Cold Pressor Test-Visual Analog Scale (CPT-VAS) and report the sensory and affective dimensions of the pain experience with the Short Form-McGill Pain Questionnaire (SF-MPQ). The CPT-VAS

questionnaire will consist of 11 items presented one at a time. Participants will be instructed to mark on a 100 mm line labeled “not at all” on one end and “extremely” at the other end indicating how they feel at that moment. The following questions will be included in the CPT-VAS: “I feel...” “Like I am coasting,” “Confused,” “Dizzy,” “Drunk,” “Elated,” “Like I am floating,” “Light-Headed,” “Nauseated,” “Sedated,” “Sleepy,” “Stimulated.” Participants will again complete the State Anxiety Inventory. Pain dissipates rapidly after removal of the extremity from the cold water. Except for the acute stress associated with the pain test, there have been no known long-term consequences of this procedure.

*Laboratory Facility:* All experimental sessions will be conducted in the Substance Use Research Center (SURC) located on the 3rd floor of the NYS Psychiatric Institute. Participants will sit in a comfortable task chair in front of a Macintosh computer. A response manipulandum (“mouse”) will be used for completion of pain rating scales and subjective-effects questionnaires.

**Table 2.** Session Schedule

Time (hr)	TIME (min)	EVENT
0900	-60	Urine, breathalyzer, breakfast
0930	-30	Baseline assessments: Mood scales, CPT
1000	0	Solution administration
1030	30	BP/HR, SRF, Mood scales
1100	60	SRF, Mood scales, CPT
1130	90	BP/HR, SRF, Mood scales
1200	120	SRF, Mood scales, CPT
1230	150	BP/HR, SRF, Mood scales
1300	180	SRF, Mood scales, CPT
1330	210	BP/HR, SRF, Mood scales, Lunch
1400	240	SRF, Mood scales, CPT
1430	270	BP/HR, SRF, Mood scales
1500	300	SRF, Mood scales, CPT
1530	330	BP/HR, SRF, Mood scales
1600	360	SRF, Mood scales, CPT
1615	375	BP/HR, SRF, Mood scales
1630	390	BP/HR, Field Sobriety Test, participant discharge

**Table 3.** Events Occurring During the Cold-Pressor Test

TIME (sec)	EVENT
-190	ST, Warm tank immersion, State
-10	ST, Vital Signs
0	Cold water immersion
180 or When hand is withdrawn	ST, Vital Signs, Pain Intensity/Bothersomeness Scales, CPT-VAS, SF-MPQ, State

*ST=skin temperature      Vital signs=blood pressure and heart rate      CPT-VAS=Visual Analog Scales  
 State=State Anxiety Inventory      SF-MPQ=Short-Form McGill Pain Questionnaire\**

*\*See descriptions of questionnaires above.*

**SAFETY MEASURES:**

The medical director of the cannabis laboratory will oversee any medical components to the study. During the sessions, a Registered Nurse and Medical Doctor will be available in the case of an emergency. During laboratory sessions, vital signs (heart rate and blood pressure) will be monitored.

Emergency medical equipment is available in our laboratory, which is located in a hospital where a full medical emergency back-up team is constantly available. We anticipate that careful participant selection, CBD dose selection and monitoring will obviate the need for such emergency care. We have been conducting inpatient and outpatient clinical pharmacology research for over 15 years and have encountered no serious adverse incidents.

**STATSTICAL ANALYSIS PLAN**

Repeated measures analysis of variance (ANOVA) with planned comparisons were used to assess cannabidiol’s dose-related effects on measures of pain and subjective drug effects associated with abuse liability. For each participant under each dose condition, pain threshold and tolerance were calculated as the difference from baseline CPT (pre-drug administration) values. Subjective pain ratings (Pain Intensity and Bothersomeness Scales) were also measured as a function of change from the baseline response. Changes scores from each of the three active cannabidiol dose strengths were compared to placebo (i. e., 0 mg vs 200 mg; 0 mg vs 400 mg; 0 mg vs 800 mg) for each of the measures specified above. Results were considered statistically significant when *p* values were equal to or less than 0.01 using Huynh-Feldt corrections (SuperANOVA, Abacus Concepts, Inc., Berkley, CA).

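### Absence of intoxication is judged only by mean comparisons at 0.01 in 18 people, so a clear reaction in about a sixth of participants at one dose would usually go unflagged

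*Combined protocol and SAP*

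**What the plan says.** The hypotheses at the end of the General Investigational Plan include a negative one: "We also hypothesize that CBD will fail to produce subjective effects of intoxication". The text there names subjective effects, with analgesia, as primary outcome measures. Earlier in the same section they are listed as secondary. That conflict does not alter this point.

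The Statistical Analysis Plan gives one method for these effects, repeated measures ANOVA with planned comparisons, used "to assess cannabidiol’s dose-related effects on measures of pain and subjective drug effects associated with abuse liability". The comparisons are 0 mg against 200, 400 and 800 mg: "Changes scores from each of the three active cannabidiol dose strengths were compared to placebo". Significance means that p "values were equal to or less than 0.01 using Huynh-Feldt corrections". The sample is 18 volunteers, each of whom receives all four conditions ("All research volunteers (N=18) will be between 21 and 50 years old").

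The plan does not state the error term of the planned comparisons, their sidedness, an equivalence margin, a confidence interval, or any count or maximum per participant. Table 2 ends each session with "Field Sobriety Test, participant discharge", and Instruments Used lists an adverse events assessment. The Statistical Analysis Plan links neither to the hypothesis.

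**The concern.** When the hypothesis is that nothing happens, a non-significant test favours it. A 0.01 threshold is strict for claiming an effect, but here it makes the favourable result easier to reach.

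A comparison of means is also weak against one particular pattern: a few participants react clearly and the rest not at all. The responders raise the variance along with the mean, so a stronger reaction need not produce a larger test statistic. The plan could then report no intoxication although several people reacted clearly at a dose and none did on placebo. Purpose, the opening section, gives the psychoactive effects and abuse potential of THC-like drugs as the reason for limited clinical interest in them, so the absence of such effects is central to the case for CBD.

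**Working it through.** The documents contain no power calculation, effect size or SD for these scales, so there is no planned figure to reproduce.

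**Inputs from the documents.** n = 18, four conditions within each participant, three comparisons with placebo, alpha 0.01. **Assumed.** Two-sided tests. k participants respond at one dose, and the other 18 − k do not change.

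**1. Paired error (17 df).** If k of n differences equal D and the rest are 0, then t = sqrt((n − 1)k/(n − k)), and D cancels. Unequal responses only lower t. With S the sum and Q the sum of squares of the differences, t = sqrt(n − 1)·S/sqrt(nQ − S²), and S² cannot exceed kQ. The critical t(17) is 2.898.

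| k of 18 | t | p |
|---|---|---|
| 3 | sqrt(17·3/15) = 1.844 | 0.083 |
| 4 | sqrt(17·4/14) = 2.204 | 0.042 |
| 5 | sqrt(17·5/13) = 2.557 | 0.020 |
| 6 | sqrt(17·6/12) = 2.915 | 0.0096 |

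Six responders are needed. The threshold is also 6 with a one-sided 0.01 test (k = 5 gives p = 0.0102) and with 16 or 17 participants tested two-sided.

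**2. Pooled dose-by-subject error (51 df), effect a at one dose.** Residual SS = a²·(3/4)·k·(1 − k/18), and t = (ak/18)/sqrt(2·MS/18). The critical t(51) is 2.676.

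- k = 3: SS = 1.875a², MS = 0.03676a², t = 0.1667/0.0639 = 2.608, p = 0.012.
- k = 4: SS = 2.333a², MS = 0.04575a², t = 0.2222/0.0713 = 3.117, p = 0.003.

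Four responders are needed. For 800 mg against placebo, the threshold is 3 if the effect is proportional to dose (p = 0.0036). If the effect is equal at 400 and 800 mg, it is 4 (p = 0.0094), or 5 when Huynh-Feldt degrees of freedom are used (k = 4 gives 0.0152, k = 5 gives 0.0061).

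**3. With background noise (simulation, effect at one dose).** Assumed: SD of the paired difference 5 mm, mean response +20, +40 or +60 mm, SD 10 mm among responders. Chance of p<=0.01:

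| k of 18 | Paired, +20 / +40 / +60 | Pooled (51 df), +20 / +40 / +60 |
|---|---|---|
| 3 | 1.1% / 0.1% / 0.0% | 11% / 21% / 25% |
| 4 | 2.5% / 0.8% / 0.1% | 26% / 63% / 85% |
| 5 | 5.8% / 5.6% / 2.7% | 48% / 94% / 99.8% |

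To see how far this depends on the assumed SD, the response can be expressed in units of the paired-difference SD, with no spread among responders. Over the values tried from 1 to 50 SD, 3 of 18 are flagged in at most about 3% of trials with paired error and 27% with pooled error.

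**4. What a count would show.** The exact (Clopper-Pearson) 95% interval is 6.4% to 47.6% for 4 of 18. For 3 of 18 it is 3.6% to 41.4%, from the 0.025 quantile of Beta(3, 16) and the 0.975 quantile of Beta(4, 15).

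**The case against.** The strongest reply concerns the error term. The plan specifies repeated measures ANOVA with a Huynh-Feldt correction. A paired contrast has one numerator degree of freedom and nothing to correct, so pooled error is at least as natural a reading. This does not settle the matter, because the correction may be meant only for the overall dose or time effects. It does rule out resting the point on paired error alone.

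A reader might therefore infer too much from the first table: that the plan cannot flag intoxication in fewer than 6 of 18 participants, however strong it is. The documents do not support that. With pooled error, 4 of 18 suffice without noise, and with noise the chance of flagging them rises with strength (26%, 63%, 85%). Even with paired error, never is the limit for strong effects: 5 responders are flagged in up to about 13% of trials at moderate strengths.

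The minority pattern is also an assumption. Placebo ratings near zero in people who do not use drugs would say nothing about what share would react to an intoxicating dose. A broad shift is equally possible, and a comparison of means suits that well.

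Finally, the sobriety test and adverse event assessment may reveal individual intoxication. This mitigates the gap but does not close it, because neither enters the planned analysis.

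**Conclusion.** The point holds in a limited form. The plan lets a non-significant mean comparison stand as evidence of no intoxication, and nothing in the Statistical Analysis Plan shows individual reactions. If an effect were confined to a minority at one dose, about a sixth of participants (3 of 18) reacting clearly would usually be missed under either error term.

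It would go too far to say that up to a quarter would be missed. Four or 5 of 18 are usually missed with paired error. With pooled error, 4 are usually missed only when responses are weak (+20 mm in the assumed case), and 5 at that strength are flagged about half the time. If the effect also appeared at lower doses in proportion to dose, 3 of 18 would reach 0.01 under pooled error without noise.

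The conclusion rests on two-sided tests, no change in non-responders apart from noise, and assumed SDs. It shows that the plan is blind to one plausible pattern. It is not evidence that CBD produces that pattern.

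**What to change.** In the Statistical Analysis Plan:

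1. State the error term of the planned comparisons, with its degrees of freedom.
2. For each drug-effect item of the Solution Rating Form, the mood scales and the CPT-VAS, report for each active dose the number of participants whose highest post-dose rating exceeds their own placebo-session highest by a margin set for that scale. Give an exact 95% interval.
3. Beside it, give the reverse count (placebo above active) with its interval. Table 2 schedules 13 post-dose Solution Rating Forms (every 30 minutes from 30 to 360, then 375), and a maximum over 13 ratings will sometimes exceed its counterpart by chance. The reverse count is the benchmark for that.
4. Require any statement that CBD lacks subjective effects to quote these counts beside the mean comparison.

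Fix the margins before unblinding. The Statistical Analysis Plan is written in the past tense, so the data may already be unblinded. In that case, report several margins and label the table post hoc.

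The cost is one descriptive table from data already collected and one margin per scale. No dose, procedure or clinical rule changes.
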